#### *Types of analyses for the primary endpoint*

##### Main analysis:

Start time for DFS: 2 year after randomization

Population: PP

##### Sensitivity analysis 1:

Start time for DFS: 2 year after randomization

Population: ITT

##### Sensitivity analysis 2:

Start time for DFS: randomization

Population: ITT

#### *Evaluation of censoring date for DFS analysis*

In case of no events and no early study termination, patients will be censored after 10.5 years. The last DFS event free day is evaluated as the maximum of the last treatment visit date and last follow up visit date including only visits with cancer status evaluation. In case of follow-up visits with documented cancer status but without a documented visit date, the lower bound of the due visit date window will be used. Follow-up visits with information whether patient is alive but without cancer status evaluation will not be used.

#### *Additional specifications*

It was possible to document the location of successive events after the first events within the event categories ‘distant metastases’ (‘Fernmetastasen’) and ‘secondary carcinoma’ (‘Zweitkarzinome’) in the eCRF. In these cases, the text “[Folge-Event]” in notes related to the location data entry fields indicate that the affected location does not belong to the first event within the respected event category. These locations will be excluded from listings of affected locations for the first events within the respective event category.

### 3.6. Secondary endpoint evaluation

All secondary endpoint analyses will be based on the ITT population. For all secondary endpoints, 2-sided log-rank tests (unstratified) will be used to test for differences between 2 additional years anastrozole versus 5 additional years anastrozole at an overall alpha level of 0.05. No multiplicity adjustment will be applied for the secondary endpoints.

#### 3.6.1. Overall survival (OS)

This is defined as the time from randomization or from two years after randomization to death due to any cause. Patients who have not died will be right-censored at the last date when they were known to be alive (date of their last assessment).

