7.3. Follow-up

After the therapy is complete, follow-up examinations are carried out at yearly intervals (+/- 6 months) for a period of 8 years in Arm A and 5 years in Arm B.

1. Clinical examinations
2. Bilateral mammogram (unilateral mammogram in the case of mastectomy)
3. Serious adverse events (see 9.1 and 9.2.4)

Written contact with the patient to obtain findings is permitted. It is also possible to check the patient's status (living or deceased) via the Central Registration Office (ZMA) or the GP. If the patient does not attend a visit for more than 2 years during the follow-up period, this results in the patient being set to the off position.

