5.5. Premature termination of the clinical study

5.5.1. Premature termination in an individual case

Reasons leading to study discontinuation are:

- Withdrawal of patient consent
- Occurrence of intolerable adverse events
- Occurrence of relapse, secondary cancer or death of the patient
- Lack of compliance or cooperation of the patient
- Serious protocol violation
- Other personal reasons for the patient (e.g. change of location); there is usually the possibility of ongoing care at another ABCSCG study site
- Patient no longer attends (lost to follow-up): the maximum time frame for this is
 - In the therapy phase: +6 months calculated from the scheduled visit date (see 6.5.)
 - In the follow-up phase: +12 months from the scheduled visit dateThe investigator must make every effort to establish contact with the patient.
- Development of hepatic, renal insufficiency

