## 3.5. Primary endpoint evaluation

### 3.5.1. Primary endpoint

Disease-free survival (DFS) is defined as the time from randomization or from two years after randomization (depending on the type of analysis, see below) to the earliest occurrence of loco-regional recurrence, distant recurrence, contralateral new breast cancer, second cancer or death, from any cause. Patients who have not had a disease recurrence or died will be right-censored at the date of their last assessment of their DFS status.

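### The OS censoring rule can be read as dropping alive reports while deaths learned from the same sources still count, and DFS has no rule for deaths long after the last cancer-status visit

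*SAP*

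**What the plan says.** **Events.** SAP 3.6.1 runs OS "to death due to any cause". The DFS list in SAP 3.5.1 ends with "second cancer or death, from any cause". Neither section limits the source of a death report or the time since the last examination.

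**Censoring.** For OS, women who have not died are "right-censored at the last date when they were known to be alive (date of their last assessment". For DFS, SAP 3.5.2 (censoring date) uses only visits with a cancer-status evaluation, and adds: "Follow-up visits with information whether patient is alive but without cancer status evaluation will not be used".

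**Sources outside visits.** Protocol 7.3 permits, but does not require, a check of the patient's "status (living or deceased) via the Central Registration Office (ZMA) or the GP", and also written contact. Amendment 1 replaces the schedule and visit list in 7.3 without quoting this paragraph, so I take it to be in force.

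**Rules that may limit late deaths.** Protocol 7.3 sets a patient to off in this case: "If the patient does not attend a visit for more than 2 years during the follow-up period". Section 5.5.1 (Amendment 1) defines loss to follow-up as "In the therapy phase: +6 months calculated from the scheduled visit date", and as 12 months after the scheduled visit in the follow-up phase. SAP 3.3.1 and 3.3.2 censor women who leave the study early, without giving the censoring date or saying whether a later known death is ignored.

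**The concern.** A status check has two possible answers. If deceased counts as an event on the date of death, and living is discarded in favour of the last examination, then whether a woman stays in the risk set depends on her outcome. Kaplan-Meier estimates and the log-rank test assume that it does not.

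Take two women last examined at year 5 and checked at year 9. One died at year 8 and is an event at year 8. The other is alive but leaves the risk set at year 5. Women who stop attending would then add deaths but no survival time.

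OS is the first secondary endpoint, and death is a component of the primary endpoint. The main OS and DFS analyses start two years after randomisation, which is when the arms separate into on-treatment and off-treatment. The trial is open-label, so a difference in attendance from that point is possible.

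**Working it through.** The plan gives no OS figure to reproduce, and its 433 design events for DFS do not bear on this point. The check is of the wording first, then of the size under assumptions.

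**1. Wording.** For DFS, SAP 3.5.1 specifies the last assessment of DFS status. For OS, SAP 3.6.1 says only last assessment. The parallel rules in 3.6.2 and 3.6.3 use a last date known to be free of the event and carry no such bracket. The detailed algorithm in 3.5.2 is for DFS only. A programmer deriving OS dates could therefore defensibly choose either date.

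**2. Inputs for size.** All are assumptions:
- true death rate λ = 0.02 a year in both arms (Protocol 2.1.2 gives 2.54% a year for years 6-10 on tamoxifen)
- follow-up of 5 to 8 years from the 2-year start, mean τ = 6.5
- 1,600 women per arm
- loss from examinations at rate μ a year; the documents give no loss rates
- every later death becomes known, although the checks are optional

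**3. Literal reading, no limit on late deaths.** At time t the deaths are the true deaths. The risk set lacks the women who have stopped attending and will survive to τ. So

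apparent hazard = λ / D, with D = 1 − (1 − e^(−μt)) · e^(−λ(τ−t)).

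At t = 3, e^(−0.02 × 3.5) = 0.9324.

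*Equal loss of 3%:* D = 1 − 0.0861 × 0.9324 = 0.9197. The apparent hazard is 0.02/0.9197 = 0.0217. Six-year mortality reads 1 − e^(−6 × 0.02175) = 12.2%, against a true 1 − e^(−0.12) = 11.3%. Simulation also gives 12.2%. The hazard ratio stays at 1.00. With 2.54% a year and equal loss of 1%, 3% or 5%, 8-year mortality reads 19.0%, 20.4% or 21.9% against 18.4%.

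*Unequal loss, constant throughout.* The null HR (B/A) is D for Arm A divided by D for Arm B:
- 4% v 2%: 0.8946/0.9457 = 0.946
- 5% v 3%: 0.8701/0.9197 = 0.946
- 6% v 3%: 0.8464/0.9197 = 0.920

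Simulations of the same cases lie between 0.91 and 0.95, with type I error of about 10%, 10% and 16%. A wider gap does more: at 2.54% deaths a year and loss of 2% v 6%, the HR moves by a factor of 1.14 and type I error is 33%. The documents give no ground for a gap that large.

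**4. Adding limits.** Suppose deaths count only within G years of the last visit, and loss differs by Δ a year for the first three years only. At time t, log HR is then roughly −Δ times the years of differential loss within the last G years. Averaged over follow-up,

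log HR ≈ −Δ × G × 3/6.5.

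- Δ = 0.02: G = 2 gives e^(−0.0185) = 0.98; G = 1 gives e^(−0.0092) = 0.99
- Δ = 0.03: G = 2 gives e^(−0.0277) = 0.97; G = 1 gives e^(−0.0138) = 0.99

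Intermediate cases by simulation: early-only differential loss with no limit gives 0.96, 0.96 and 0.94; constant differential loss with a 2-year limit gives 0.95-0.97, with type I error of 5-7%.

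**5. Symmetric handling.** If alive and death reports are both used to a common date, or both ignored after the last visit, simulated HRs are about 1.00 and type I error is 4.5-5.3%, even with unequal attendance.

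**6. DFS.** With assumed rates of 2.5% a year for relapse, 1.5% for death without relapse and 12% for death after relapse, complete ascertainment and no limit, the three unequal-loss cases give null HRs of about 0.97, 0.97 and 0.95.

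**The case against.** The strongest reply is that SAP 3.6.1 already says the right thing. Its main clause is the last date known alive, and nowhere does the SAP say that alive reports are discarded for OS. The sentence excluding alive-only contacts sits under the DFS censoring heading and calls those contacts follow-up visits, so they could count as assessments for OS. A reader might infer that the plan certainly discards alive reports for OS; the text does not support that. What stands is that the bracket equates two dates that can differ.

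For DFS, an alive report does not show freedom from disease, so the censoring rule is not an error. Only the missing rule on late deaths remains.

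The off-study, lost-to-follow-up and early-termination rules may also exclude late deaths. The woman last examined at year 5 would be off after year 7, so her death at year 8 is arguably not counted. That registry deaths count at all is inferred from the any-cause definitions. This reply has force, but no rule states the consequence for a known later death.

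A reader might also infer a bias in favour of 5 years of treatment. The documents do not establish this. Amendment 1 gives Arm A the same examinations at months 36, 48 and 60. In that period the lost-to-follow-up window is 6 months for women on therapy and 12 months for those in follow-up, which could remove Arm B women sooner and push the other way.

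**Conclusion.** The point holds as an ambiguity with a one-sided literal reading, not as a proven bias. On that reading, mortality is somewhat overstated in both arms: about one percentage point at six years under 2% deaths and 3% equal loss a year. The comparison is distorted only if attendance differs by arm.

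With more loss assumed in Arm A, the null OS HR (B/A) runs from about 0.92-0.94 (constant differential loss, complete registry status, no limit) to about 0.97-0.99 (differential loss for three years, deaths counted within 1-2 years of the last visit). It is 1.00 with equal loss. If the assumed loss is reversed, so is the direction. Where the trial falls depends on loss rates, on use of the optional checks and on how the off-study rules are applied, none of which the documents settle. The lower figures should therefore not be quoted as the expected effect. The change is still worth making, because it is cheap and removes a choice that could otherwise be made after the data are seen.

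**What to change.** **SAP 3.6.1.** Delete the bracket that equates the date with the last assessment. Censor OS at the latest recorded date known alive from any source (visit, letter, GP, registration office), up to the data cut-off and the 10.5-year cap, in the same way in both arms. State whether a death known after early termination or off status counts.

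**SAP 3.5.2.** Keep the main DFS rule. Add one sensitivity analysis in which a woman whose death without prior relapse falls beyond a pre-stated gap after her last cancer-status visit is censored at that visit. Eighteen months (one yearly interval plus the 6-month visit window) is one option; it is not a figure from the documents. State how the gap relates to the 12-month and more-than-2-years rules, which need reconciling in any case.

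**Cost.** SAP wording and one extra run. A few late deaths drop out of that sensitivity analysis only. One limit remains: the OS rule equalises only the reports that are recorded. If deaths are notified spontaneously and survival is not, some one-sidedness persists unless status is sought alike in both arms.

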##### Main analysis

Start time for OS: 2 year after randomization

##### Sensitivity analyses

Start time for OS: randomization

#### 3.6.2. Time to new contralateral breast cancer

This is defined as the time from randomization or from two years after randomization to first occurrence of new contralateral breast cancer. Subjects without contralateral breast cancer event would be censored at last date when they were known to be contralateral breast cancer free.

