10.4. Efficacy analysis

The final analysis is carried out according to the intent-to-treat principle of all randomised patients who meet the inclusion and exclusion criteria, have at least one follow-up examination after randomisation, and have survived for 2 years relapse free. They will be assigned to the group into which they were randomised regardless of whether they actually received the therapy or which one.

The graphical representation of the therapeutic effect on the primary and secondary target variables (DFS, overall survival and occurrence of secondary cancers, contralateral breast cancer and fractures) is based on the survival functions according to Kaplan and Meier (1958). The differences between the two study arms are tested using the log-rank test (Mantel (1966)).

In addition, the regression model according to Cox (1972) is used in an exploratory way to examine whether the consideration of additional prognostic factors modifies the results of the log-rank tests. This takes into account primarily the stratification criteria of the randomisation but also other prognostic factors. Differences in the therapy are quantified using hazard ratios (relative mortality risk during therapy compared with the control group). In addition, possible interactions of the therapy with other prognostic factors are examined. In the event of significant interactions, subgroup analyses are carried out.

All calculations are performed using the statistical software SAS® (Statistical Analysis Software; version 8) and all tests are two-tailed, where $p \leq 0.05$ is deemed statistically significant.

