##### Main analysis

Start time for time until new contralateral breast cancer: 2 year after randomization

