#### 3.6.3. Time to secondary carcinoma

This is defined as the time from randomization or from two years after randomization to first occurrence of new secondary cancer without new breast cancer (local or contralateral). Subjects without secondary cancer event would be censored at last date when they were known to be secondary cancer free.

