### 3.6.4. Time to first clinical fracture

This is defined as the time from two years after randomization to first clinical fracture. Patients without clinical fractures were censored at their last therapy visit (maximum approximately 5 years after randomization).

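### Kaplan-Meier curves for second cancer, contralateral breast cancer and fracture treat death as censoring, so any risk read from them is somewhat too high

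*SAP*

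**What the plan says.** Protocol section 10.4 states that the graphical display of the therapeutic effect "is based on the survival functions according to Kaplan and Meier (1958"). It lists the variables concerned as "DFS, overall survival and occurrence of secondary cancers, contralateral breast cancer and fractures". The arms are compared by log-rank test, and therapy differences are quantified by hazard ratios.

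SAP section 3.6 keeps the test: "2-sided log-rank tests (unstratified) will be used to test for differences". It does not restate the method of display, and SAP section 4, on changes from the protocol, neither drops Kaplan-Meier nor adds another estimator.

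The SAP's censoring rules are:

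- Contralateral cancer (3.6.2): "Subjects without contralateral breast cancer event would be censored at last date when they were known to be contralateral breast cancer free". The main analysis starts the clock late: "Start time for time until new contralateral breast cancer: 2 year after randomization". Starting at randomisation is a sensitivity analysis.
- Second cancer (3.6.3): "Subjects without secondary cancer event would be censored at last date when they were known to be secondary cancer free". The clock starts are the same.
- Fracture (3.6.4): "This is defined as the time from two years after randomization to first clinical fracture". Women without a fracture are censored at their last therapy visit, at most about 5 years after randomisation.

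None of these rules mentions death. Neither document mentions competing risks or cumulative incidence.

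**The concern.** A woman who has died cannot later have a second cancer or a fracture. Kaplan-Meier with deaths censored treats her as if she still could, and spreads her future risk over the women who remain. One minus Kaplan-Meier then describes a setting in which nobody dies, and it is higher than the proportion of women who have the event. DFS and overall survival do not have this problem, because death is an event in both.

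These three endpoints are stated secondary objectives. They are also the figures a patient would weigh when choosing between 2 and 5 further years of treatment. If risks are read off the curves, each arm's risk is too high. With similar mortality in both arms, the absolute difference between the arms is too large as well.

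**Working it through.** The plan gives no expected rate for any of the three endpoints. Its DFS assumption is the only internal anchor, so that is reproduced first.

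**1. DFS hazards.** Protocol section 10.1 assumes 0.937 and 0.916 event-free 3 years after the change of therapy, with exponential survival.

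- −ln(0.937)/3 = 2.17% a year
- −ln(0.916)/3 = 2.92% a year
- Ratio 2.92/2.17 = 1.35, as stated

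**2. Ceiling on competing mortality.** DFS counts second cancer and death from any cause. Every woman who has a second cancer, or dies without one, has therefore had a DFS event. With constant hazards, the second-cancer rate plus the rate of death without second cancer cannot exceed the DFS hazard. With second cancer at an assumed 1.0% a year (not in the documents), the ceiling is:

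- 2.17 − 1.00 = 1.17% a year
- 2.92 − 1.00 = 1.92% a year

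**3. Formulas.** Let a be the event rate, d the death rate and T the window.

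- Kaplan-Meier risk = 1 − exp(−aT)
- Cumulative incidence = a/(a+d) × [1 − exp(−(a+d)T)]

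**4. Second cancer, a = 1.0%, T = 8 years** (year 2 to year 10).

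- Kaplan-Meier: 1 − exp(−0.08) = 7.69%
- d = 1.17%: 0.01/0.0217 × [1 − exp(−0.1736)] = 7.34%; excess 0.34 points, 4.7% relative
- d = 1.92%: 0.01/0.0292 × [1 − exp(−0.2336)] = 7.13%; excess 0.55 points, 7.8% relative

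The result depends on the assumed rate, because the rate moves the ceiling. At 0.6% a year the ceiling is 1.57 to 2.32% and the relative excess 6.4 to 9.5%. At 1.2% a year it is 0.97 to 1.72% and 3.9 to 6.9%.

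**5. Contralateral cancer, a = 0.4% (assumed), T = 8, same d.**

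- Kaplan-Meier 3.15%; cumulative incidence 3.01% to 2.92%
- Excess 0.14 to 0.23 points, 4.7 to 7.8% relative

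Deducting only contralateral cancer from the DFS hazard would allow d of 1.77 to 2.52% and an excess of 7.2 to 10.4%. That is an outer limit: it leaves no room for women alive with recurrence or another cancer.

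**6. Fracture, T = 3 years** (year 2 to about year 5). Protocol Table 2 gives 5.8% on anastrozole. The text puts mean time on therapy and in the study at 30 to 36 months. Taking 2.75 years, a = 5.8/2.75 = 2.1% a year. The same d is used here as an assumption, since fracture is not a DFS event.

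- Kaplan-Meier 6.13%; cumulative incidence 6.03% to 5.96%
- Excess 0.10 to 0.17 points, about 2 to 3% relative

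**7. Effect on a difference between arms.** As an illustration, take second-cancer rates of 1.0% and 1.35% with d = 1.17% in both arms, which fits within both DFS hazards. The 8-year difference is 10.24 − 7.69 = 2.55 points by Kaplan-Meier and 9.78 − 7.34 = 2.44 points by cumulative incidence. The gap is about 0.1 points.

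**The case against.** The strongest defence is that the plan promises very little that depends on these curves. Kaplan-Meier appears only for graphical display in the protocol, treatment effects are expressed as hazard ratios, and the only method SAP section 3.6 specifies is the log-rank test. For that test, censoring deaths is correct: it compares cause-specific hazards. Neither document commits to quoting a risk or a risk difference at a time point. All of this stands, and it limits the point to the curves and to whatever is read from them.

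Three stronger readings are tempting, and the documents do not support them.

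- **An excess of about 10% or more.** A reader might take the annual fatalities in protocol section 2.1.2 (2.54% and 2.16%, mean 2.35%) as competing mortality and obtain 7.69% against 7.02% for second cancer. But 1.00 + 2.35 = 3.35% a year exceeds the whole DFS hazard in either arm, which already counts both events. The table is also not stated to be all-cause mortality. Its fatalities exceed recurrences in years 6 to 10, which suggests deaths after earlier relapse, whereas this trial enrols relapse-free women.
- **Ten years of exposure for all three endpoints.** Fracture runs for about 3 years. The main cancer analyses run for about 8 to 8.5 years, and only the sensitivity analyses from randomisation reach 10.
- **A markedly older population.** Amendment 2 did remove the upper age limit, but in October 2008, with recruitment running from December 2003 to June 2010. No count of women over 80 is given, so the effect on mortality cannot be sized.

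**Conclusion.** The point holds as a refinement of reporting. Under the planned method, risks read from the curves for second cancer and contralateral cancer would be about 5 to 8% too high in relative terms over 8 years. That is 0.3 to 0.6 points for second cancer and 0.1 to 0.2 for contralateral cancer. For fracture the excess is about 0.1 to 0.2 points and close to negligible.

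The direction is certain wherever event-free women die and are censored. The size rests on constant hazards, on assumed rates of 1.0% and 0.4% a year, and on competing mortality at the ceiling set by the trial's own DFS assumption, with its exponential form carried from 3 to 8 years. Mortality below that ceiling would make the excess smaller.

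A reader might infer that the treatment comparison is biased. It is not: the log-rank tests and hazard ratios remain valid as cause-specific comparisons.

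**What to change.** In protocol section 10.4 and SAP sections 3.6.2 to 3.6.4, replace the Kaplan-Meier display with Aalen-Johansen cumulative incidence curves by arm, treating death without the event as a competing event. The gain lies mainly in the two cancer endpoints; fracture should follow for consistency. State explicitly how deaths are handled. Keep the log-rank test and label it as a comparison of cause-specific hazards. DFS and overall survival stay on Kaplan-Meier.

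The cost is a little more programming and no new data. The curves will not be directly comparable with trials that used Kaplan-Meier for these endpoints. Gray's test is optional and not needed: the existing test is valid, and SAP section 3.6 applies no multiplicity adjustment to the secondary endpoints.
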